### **Guideline for Documenting Community Led Model**

Interim findings from the qualitative work that informs community-led models. Views on community-led distribution

1. Views on feasibility mixed but mostly positive. Foster control and ownership ‘we know who is who’ and where they are located. They also talked about potential challenges: incentives and resources, corrupt inclinations by leaders in the community. Some might sell the kits. Kept on referring to external support that was technical and financial.
2. Who should distribute – definitely not community leaders. Too old, too corrupt, have other people doing things for them; church leaders thought to have multiple roles and would have challenges in balancing work (apostolic sect values could be a barrier). Preference for non-leaders like village health workers, young people, committed men and women.
3. Suggested roles for distributors – distribute, record keeping, counselling and education on ST and linkage.
4. Desired characteristics: volunteer driven by intrinsic motivation, literate, good conduct, member of the local community. Want monetary incentives. Compensate time – minority view that it should not be incentivised.
5. Who should plan – multiple stakeholders, community leaders, HCWs technical support, PSI Zimbabwe was mentioned as source of training and incentives; MoH also; CLD committee to monitor process and social harms, general community – for participation and transparency. We should know selection process. Planning meetings where whole community is present
6. Social harms and violence to the distributor, partner violence, stigma and discrimination were also raised.
7. Sustainability was felt possible depending on kit supply (which must not be erratic) and community leader support. Reliable incentives and need for expert technical support from outside. Didn’t feel test kits should be for sale.
8. Long standing community squabbles might be a threat.
9. KIIs MOHCC provincial, district and ward, AIDS committees etc.

### **Minimum definition of community-led approach. Common principles**

1. A participatory process
2. Community takes leading role
  - a. Community decides who distributes and how
  - b. Community conducts distribution
  - c. Communities collect and use data
  - d. Community frames messaging and communication, disseminates learning
  - e. Community decides on motivation and incentives
3. Community has access to
  - a. Quality test kits that are in stock
  - b. Technical assistance
  - c. Training

- d. Knowledge sharing
- e. Resources in with sustainability plan and workshop

**Template for documenting each community model**

- 1. Date
- 2. Country
- 3. Community definition
- 4. Target population
- 5. Community structure for governance e.g. neighbourhood health committee
- 6. Distribution model and points
- 7. Typology of distributor
- 8. Training duration
- 9. Supervision
- 10. How distributors are motivated
- 11. Sustainability plan
- 12. Inputs what is going into the model – training, number of workshops etc, process of model development, funds, equipment and materials

## **Appendix 5: Facility Costing Survey Questionnaire**

### **Costs to the Individual of Accessing HIV testing services (All models)**

I would now like to ask you some questions about the costs you incurred for accessing this HIV test.  
Do you have any questions before we begin?

1. How did you get to the testing place/location from home?
  - a. Walked
  - b. by Taxi
  - c. By bus
  - d. by own car
  - e. by Bicycle
  - 1.1. How long did it take you to reach the testing place/facility? \_\_\_\_\_ hours: \_\_\_\_\_ minutes
  - 1.2. Did you pay for transport to get to the testing place/facility from home? a. Yes  b. No
  - 1.3. How much did you pay to get to the testing place including fuel if you used your own car?  
\_\_\_\_\_
2. For how long did it take to have your HIV test? Including waiting to be tested and given your results? \_\_\_\_\_ hours: \_\_\_\_\_ minutes
  - 2.1. What method did you use to have your HIV test? a. HIVST  b. Finger prick by counsellor
3. Did you have to pay any fees to take the HIV test? This includes consultation, registration, the test kit, and counselling. a. Yes  b. No 
  - 3.1. How much in fees did you pay to take the HIV test?
4. Was this visit primarily to be tested for HIV? a. Yes  b. No 
  - 4.1. If no, is the time given in Q 2 exclusively for HIV testing? a. Yes  b. No
  - 4.2. If no how long did it take, exclusively, to have your HIV test done? \_\_\_\_\_ hours:  
\_\_\_\_\_ minutes
5. Did you have to purchase food outside the home because of your HIV test? b. Yes  b. No 
  - 5.1. How much did you pay for food? \_\_\_\_\_
6. Did you incur other costs related to your HIV test? a. Yes  b. No 
  - 6.1. How much did you pay for other costs? \_\_\_\_\_
7. Did you have to pay for anyone to cover your regular duties while getting the HIV test? This includes to take care of your children, supervise your shop, or perform your regular economic activities. a. Yes  b. No 
  - 7.1. How much did you pay for someone to cover your regular duties? \_\_\_\_\_
8. How much would you have earned during the time you took off to get tested for HIV?  
\_\_\_\_\_
9. Who primarily provided the money to support the costs of accessing the test? a. Household member   
b. relative/friend  c. other (specify: \_\_\_\_\_)
10. Were any of these costs covered by anyone else, such as, insurance or your employer? a. Yes   
b. No

### **Health Care Utilization and Costs to the Individual of Accessing HIV Care (ART model)**

I would now like to ask you some questions about your access to health care services in the last one year and how much it costs. Do you have any questions before we begin?

1. Are you currently on ART? a. Yes  b. No   
a. If yes how long have you been on ART? \_\_\_\_\_
2. Are you currently taking Septrin? a. Yes  b. No
3. If yes to Q1 what drugs are you taking? \_\_\_\_\_  
(Check the card for quantities dispensed in the last 12 months)
4. How frequent do you come to get your drugs? a. Monthly  b. Bi-monthly  c. Quarterly   
d. other (specify: \_\_\_\_\_)
5. For this visit, how did you get to the facility from home?  
a. Walked  b. By Taxi  c. By bus  d. By own car  e. By Bicycle   
5.1. How long did it take you to reach the facility? \_\_\_\_\_ hours: \_\_\_\_\_ minutes
6. Did you pay for transport to get to the facility from home? a. Yes  b. No   
6.1. How much did you pay to get to the testing place including fuel if you used your own car?  
\_\_\_\_\_
7. How long did you have to wait before you were attended to? \_\_\_\_\_ hours: \_\_\_\_\_ minutes
8. For how long did it take to receive care services including any laboratory tests? \_\_\_\_\_ hours:  
\_\_\_\_\_ minutes
9. Did you have to pay any fees to access ART drugs a. Yes  b. No   
9.1. How much in fees did you pay to access the drugs? \_\_\_\_\_
10. Did you have to purchase food outside the home because of accessing HIV care services? a. Yes   
b. No  
10.1. How much did you pay for food? \_\_\_\_\_
11. Did you incur other costs related to this visit to the facility? a. Yes  b. No   
11.1. How much did you pay for other costs? \_\_\_\_\_
12. Did you have to pay for anyone to cover your regular duties while access HIV care services? This includes to take care of your children, supervise your shop, or perform your regular economic activities. a. Yes  b. No   
12.1. How much did you pay for someone to cover your regular duties? \_\_\_\_\_
13. How much would you have earned during the time you took off to access HIV care services?  
\_\_\_\_\_
14. Who primarily provided the money to support the costs of accessing HIV care services? a.  
Household member  b. relative/friend  c. other (specify: \_\_\_\_\_)

#### A. WTP Questions: Potential Users

##### 1. HIV Self-testing

QUESTION	RESPONSE CODE
Have you heard of the HIV self-testing method?	Yes 1 No 2 Don't Know 99
Are you interested in using this method in your next HIV test?	Yes 1 No 2 Don't Know 99
READ TO CLIENT:	
I would now like to ask you some questions about the possible price of this product. In answering these questions, please bear in mind the following:	
1. Assume that your income will stay the same even if the provider prices change. 2. Alternatives do exist for HIV testing services.	
If the price of this product was ZMW10.00, would you purchase this service from the provider?	Yes 1 No 2 Don't Know 99
If the price of this product was ZMW15.00, would you purchase this service from the provider?	Yes 1 No 2 Don't Know 99
If the price of this product was ZMW20.00, would you purchase this service from the provider?	Yes 1 No 2 Don't Know 99
If the price of this product was ZMW30.00, would you purchase this service from the provider?	Yes 1 No 2 Don't Know 99
If the price of this product was ZMW50.00, would you purchase this service from the provider?	Yes 1 No 2 Don't Know 99
What would be the highest amount you would be willing to pay for this product from the provider?	Amount _____
If you were interested in using this product but were unable to pay the provider's price, what would you do?	Go without testing 1 Go somewhere else for this service 2

	Other: specfy_____	88
	I don't know	99
You said you would not have an HIV test if you were unable to pay the provider's price. Would you use another HIV testing method?	Yes: specify _____	1
	No	2
	I don't know	99
Where would you go?  DO NOT READ CHOICES CODE ALL MENTIONED	Public health facility NGO Private Sector Other: specfy_____	1 2 3 88
	I don't know	99

## B. WTP for Amenities and Quality Improvements

### a. WTP for Reduced Waiting Time

QUESTION	RESPONSE CODE
How long did you have to wait before you were seen by clinic staff?	___ hours ___ minutes
Do you consider this wait to be excessive, reasonable, or short?	Excessive 1 Reasonable 2 Short 3
Suppose we could cut your waiting time in half but your consultation would cost ZMW10.00, would you be willing to pay for this improvement?	Yes 1 No 2 Don't know 99

Suppose we could cut your waiting time in half but your consultation would cost ZMW15.00, would you be willing to pay for this improvement?	Yes 1 No 2 Don't know 99
Suppose we could cut your waiting time in half but your consultation would cost ZMW20.00, would you be willing to pay for this improvement?	Yes 1 No 2 Don't know 99
Suppose we could cut your waiting time in half but your consultation would cost ZMW30.00, would you be willing to pay for this improvement?	Yes 1 No 2 Don't know 99
Suppose we could cut your waiting time in half but your consultation would cost ZMW50.00, would you be willing to pay for this improvement?	Yes 1 No 2 Don't know 99
What is the most you would be willing to pay for your consultation if this Improvement was made?	Amount _____

*b. WTP for Counselling*

QUESTION	RESPONSE CODE
How much time did your provider spend with you explaining procedures and counselling you on your HIV related issues?	___ hours ___ minutes
Do you consider the amount of time the provider spent with you to be excessive? Reasonable, or short?	Excessive 1 Reasonable 2 Short 3
Suppose we could increase counselling time you could spend with your provider by an additional 10 minutes but your consultation would cost ZMW10.00, would you be willing to pay for this improvement?	Yes 1 No 2 Don't know 99
Suppose we could increase counselling time you could spend with your provider by an additional 10 minutes but your consultation would cost ZMW15.00, would you be willing to pay for this improvement?	Yes 1 No 2 Don't know 99
Suppose we could increase counselling time you could spend with your provider by an additional 10 minutes, but your consultation would cost ZMW20.00, would you be willing to pay for this improvement?  Suppose we could increase counselling time you could spend with your provider by an additional 10 minutes but your consultation would cost ZMW30.00, would you be willing to pay for this improvement?	Yes 1 No 2 Don't know 99  Yes 1 No 2 Don't know 99
Suppose we could increase counselling time you could spend with your provider by an additional 10 minutes but your consultation would cost ZMW50.00, would you be willing to pay for this improvement?	Yes 1 No 2 Don't know 99

What would be the highest amount you would be willing to pay for your Consultation if this improvement were made?	Amount

*WTP for Clinic Improvements*

QUESTION	RESPONSE CODE																																			
READ AND SHOW CARD TO CLIENT: The clinic management is thinking of improving the waiting area at the clinic. This section lists 5 possible improvements for this clinic. Please rank each improvement from 1 to 5, where 1 means that the improvement is NOT AT ALL IMPORTANT to you and 5 means the improvement is VERY IMPORTANT to you.																																				
a. Waiting area with people for all services b. Separate waiting area for HIV services only c. More comfortable chairs in the waiting room d. Air-conditioning in the waiting room e. A TV in the waiting room	
  
 NOT Very Important	
 
 Very Important	 	 	 	Important	
   
 5	4	3	2	1	
  
	NOT Very Important					Very Important				Important	5	4	3	2	1	5	4	3	2	1	5	4	3	2	1	5	4	3	2	1	5	4	3	2	1
NOT Very Important																																				
Very Important				Important																																
5	4	3	2	1																																
5	4	3	2	1																																
5	4	3	2	1																																
5	4	3	2	1																																
5	4	3	2	1																																
NOTE: IF RESPONDENT HAS TWO OR MORE SELECTIONS WITH THE SAME HIGHEST SCORE, ASK THE CLIENT WHICH AMENITY IS MOST IMPORTANT TO HER/HIM; IF THE CLIENT HAD TO CHOOSE, WHICH WOULD THE CLIENT CHOOSE.																																				
If "a" is most important GO TO .....																																				
If "b" is most important GO TO .....																																				
If "c" is most important GO TO .....																																				
If "d" is most important GO TO .....																																				
If "e" is most important GO TO .....																																				

You ranked Waiting area with people for all services as the most important improvement. Would you be willing to pay your ZMW10.00 for next visit if the clinic added this amenity?	Yes No Don't know	1 2 99
Would you be willing to pay ZMW15.00 for your next visit if the clinic added this amenity?	Yes No Don't know	1 2 99
Would you be willing to ZMW20.00 for your next visit if the clinic added this amenity?	Yes No Don't know	1 2 99
Would you be willing to pay ZMW30.00 for your next visit if the clinic added this amenity?	Yes No Don't know	1 2 99
Would you be willing to pay ZMW50.00 for your next visit if the clinic added this amenity?	Yes No Don't know	1 2 99
What would be the highest amount you would be willing to pay for your consultation if this improvement were made?	Amount _____	
<hr/>		
You ranked Separate waiting area for HIV services only as the most important improvement. Would you be willing to pay ZMW10.00 for your next visit if the clinic added this amenity?	Yes No Don't know	1 2 99
Would you be willing to pay ZMW15.00 for your next visit if the clinic added this amenity?	Yes No Don't know	1 2 99
Would you be willing to ZMW20.00 for your next visit if the clinic added this amenity?	Yes No Don't know	1 2 99
Would you be willing to pay ZMW30.00 for your next visit if the	Yes	1

clinic added this amenity?	No	2
	Don't know	99
Would you be willing to pay ZMW50.00 for your next visit if the clinic added this amenity?	Yes	1
	No	2
	Don't know	99
What would be the highest amount you would be willing to pay for your consultation if this improvement were made?	Amount _____	
You ranked More comfortable chairs in the waiting room services as the most important improvement.	Yes	1
Would you be willing to pay ZMW10.00 for your next visit if the clinic added this amenity?	No	2
	Don't know	99
Would you be willing to pay ZMW15.00 for your next visit if the clinic added this amenity?	Yes	1
	No	2
	Don't know	99
Would you be willing to ZMW20.00 for your next visit if the clinic added this amenity?	Yes	1
	No	2
	Don't know	99
Would you be willing to pay ZMW30.00 for your next visit if the clinic added this amenity?	Yes	1
	No	2
	Don't know	99
Would you be willing to pay ZMW50.00 for your next visit if the clinic added this amenity?	Yes	1
	No	2
	Don't know	99
What would be the highest amount you would be willing to pay for your consultation if this improvement were made?	Amount _____	
You ranked Air-conditioning in the waiting room as the most important improvement.		

Would you be willing to pay ZMW10.00 for your next visit if the clinic added this amenity?	Yes No Don't know	1 2 99
Would you be willing to pay ZMW15.00 for your next visit if the clinic added this amenity?	Yes No Don't know	1 2 99
Would you be willing to ZMW20.00 for your next visit if the clinic added this amenity?	Yes No Don't know	1 2 99
Would you be willing to pay ZMW30.00 for your next visit if the clinic added this amenity?	Yes No Don't know	1 2 99
Would you be willing to pay ZMW50.00 for your next visit if the clinic added this amenity?	Yes No Don't know	1 2 99
What would be the highest amount you would be willing to pay for your consultation if this improvement were made?	Amount _____	
You ranked TV as the most important as the most important improvement. Would you be willing to pay ZMW10.00 for your next visit if the clinic added this amenity?	Yes No Don't know	1 2 99
Would you be willing to pay ZMW15.00 for your next visit if the clinic added this amenity?	Yes No Don't know	1 2 99
Would you be willing to ZMW20.00 for your next visit if the clinic added this amenity?	Yes No Don't know	1 2 99
Would you be willing to pay ZMW30.00 for your next visit if the clinic added this amenity?	Yes	1

	No	2
	Don't know	99
Would you be willing to pay ZMW50.00 for your next visit if the clinic added this amenity?	Yes	1
	No	2
	Don't know	99
What would be the highest amount you would be willing to pay for your consultation if this improvement were made?	Amount	_____
END INTERVIEW AND THANK RESPONDENT FOR HER TIME.		

#### **Willingness to accept (WTA) Questions: Potential community distributors**

##### *b. HIVST Price*

QUESTION	RESPONSE CODE
READ TO CLIENT:	
I would now like to ask you some questions about the possible price of this product. In answering these questions, please bear in mind the following:	
1. Assume that you will continue receiving HIVST kits free of charge. 2. Alternatives do exist for HIV testing services.	
How much would you charge to distribute a kit to potential users?	Amount _____

##### *a. WTA for incentives*

QUESTION	RESPONSE CODE
Suppose supplies decide to give you any form of non-monetary incentives, would	Yes 1 No 2
You still charge for distributing HIVST kits	

	Don't know	99
How much would you charge for distributing one kit?	Amount _____	

*WTP for change in HIVST demonstration time*

QUESTION	RESPONSE CODE
How long did you take to demonstrate how to do HIV Self-Testing?	_____ hours _____ minutes
Do you consider this wait to be excessive, reasonable, or short?	Excessive 1 Reasonable 2 Short 3
Suppose we could cut your waiting time in half but all other things remain the same, how much would you charge for distributing one kit?	Amount _____

c. *WTP for Reduced Waiting Time*

QUESTION	RESPONSE CODE
Suppose the government decide to pay you for distributing kits to the community members, will you be distributing kits for free?	Excessive 1 Reasonable 2 Short 3
Suppose the government offers you to pay you ZMW1.00 per kit distributed, would you continue distributing kits for free?	Yes 1 No 2 Don't know 99
Suppose the government offers you to pay you ZMW2.00 per kit distributed, would you continue distributing kits for free?	Yes No

	Don't know
Suppose the government offers you to pay you ZMW3.00 per kit distributed, would you continue distributing kits for free?	Yes No Don't know
Suppose the government offers you to pay you ZMW4.00 per kit distributed, would you continue distributing kits for free?	Yes No Don't know
Suppose the government offers you to pay you ZMW5.00 per kit distributed, would you continue distributing kits for free?	Yes No Don't know
What is the maximum amount you would be willing to accept to be paid?	Amount _____

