### **2.1 Study aim**

The overall aim of this study is to inform early scale-up and guideline development for approaches to distributing HIVST in Zambia through in-depth evaluation of five promising distribution models. The evaluation will use a mixed method approach using qualitative, economic and quantitative data.

The qualitative analysis will explore user and provider perspectives and experiences, and the contextual factors that affect the acceptability of HIVST and subsequent post-test services where HIVST are distributed through different approaches. Data on social harms and risk factors for social harms will also be explored.

The quantitative components of this study will include using routinely collected programmatic data to describe the process of HIVST distribution and, in the two secondary distribution models, recruitment of larger cohorts of index patients (attending ANC and HIV testing and treatment services). The cohorts will investigate who is reached through secondary distribution and evaluate the factors associated with a successful secondary distribution. The cohorts will allow us to measure the proportion of HIVST kit recipients who link to confirmatory testing, prevention or care services. Accuracy of secondary distribution HIVST kits will not be evaluated here but is being included in a parallel STAR study in Malawi.

The economic analysis will involve programmed expenditure review, complemented by field observations, to calculate the health systems costs. Field observations help in generating allocation factors across activities and shared resources as well as identifying associated economic costs of distributing HIVST. We also conduct interviews with testers, including potential testers, to assess patient's costs of accessing HIV services as well as their willingness to pay for HIVST. We also conduct interviews with distributors, for community-led models, to assess their willingness to accept distribution of the kits.

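### The distributor willingness-to-accept block closes by asking for the maximum payment instead of the minimum, and its ZMW1–5 ladder is ambiguous about what distributing for free means

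*Protocol*

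**What the plan says.** The commitment is one sentence in Protocol section 2.1: "We also conduct interviews with distributors, for community-led models, to assess their willingness to accept distribution of the kits". The instrument is in Appendix 5, under the willingness-to-accept questions for potential community distributors. It contains:

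- **Three open-ended charge items.** The first, under the HIVST price heading, asks "How much would you charge to distribute a kit to potential users". The second, asked after supposing non-monetary incentives, is "How much would you charge for distributing one kit". The third repeats the question on the supposition that a waiting time is halved.
- **A payment block of seven items**, headed as willingness to pay for reduced waiting time. The lead item is "Suppose the government decide to pay you for distributing kits to the community members, will you be distributing kits for free", with the printed codes Excessive / Reasonable / Short. Five bids follow at ZMW1, 2, 3, 4 and 5. The lowest is "Suppose the government offers you to pay you ZMW1.00 per kit distributed, would you continue distributing kits for free" and the highest is "Suppose the government offers you to pay you ZMW5.00 per kit distributed, would you continue distributing kits for free", with Yes / No / Don't know as options. The closing item is "What is the maximum amount you would be willing to accept to be paid".

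**The concern.** A payment ladder followed by an open amount is the usual way to elicit a reservation price. Earlier in Appendix 5, the willingness-to-pay ladders properly end by asking for the highest amount the client would pay. The distributor block keeps that end of the scale, although the direction of payment is reversed and the quantity of interest is now the lowest amount. Together with the waiting-time heading and the misplaced codes, this suggests a willingness-to-pay template that was not fully adapted.

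Payment of distributors is a live question in this study. Appendix 1 plans no formal remuneration for the community shops in the society-run sites. The interim findings in the Appendix 4 guideline for documenting the community-led model report a wish for monetary incentives and link sustainability to reliable incentives. A figure that is too high, or that cannot be read, would misinform that discussion.

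**Working it through.** No willingness-to-accept estimate, sample size or precision is stated, so there is no figure to reproduce. The check is whether each item's answer identifies the lowest acceptable payment per kit.

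**Closing item.** Let m be the smallest payment per kit that the distributor would accept. Any payment of m or more is acceptable, so a largest acceptable amount is at least m and has no natural ceiling. As an illustration, assume m = ZMW2. Every answer from ZMW2 upwards is then consistent with the question, and none below ZMW2 is. If some respondents silently correct the question and give their minimum, the answers mix two quantities and cannot be separated afterwards.

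**Ladder.** The bids can be read in two ways.

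| Reading of *for free* | Yes at ZMW x | No at ZMW x | Does the switch locate m? |
|---|---|---|---|
| Free to the client | x is enough to keep giving kits without charge | x is not enough | Yes: ≤1, 1–2, 2–3, 3–4, 4–5 or >5 |
| Unpaid | would go on without the payment just offered | would not go on unpaid, or would take the payment | No |

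With m = ZMW2 and the first reading, the answers are No at ZMW1 and Yes from ZMW2 to ZMW5, which brackets m between 1 and 2. With the second reading, the same person may answer No at every bid, because the payment would be taken when offered. Five No answers therefore mean a minimum above ZMW5 on one reading, and are compatible with a minimum of ZMW1 or less on the other. Nothing recorded shows which reading the respondent used.

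Appendix 1 does not settle it. In the society-run sites, shop distributors give kits to community members without charge and also receive no formal pay, so both meanings describe their situation.

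**Lead item.** It is a yes/no question with the same ambiguity, and its printed codes are ratings of a length of time. No answer to it can be coded as printed.

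**Charge items.** All three return an amount per kit and avoid both wording faults. Respondents are told to assume that they keep receiving kits free, so the stated charge is for the distribution task. The items remain proxies:

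- The first is introduced as a price of the product and names potential users, so it may be read as a price to clients.
- The second is conditional on non-monetary incentives.
- The third follows a question on demonstration time but refers to a waiting time.

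An asking price is also likely to lie above the lowest amount the person would settle for. That last point is a judgement, not something the protocol states.

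**The case against.** The best defence concerns the ladder. Appendix 1 uses free in the sense of free to community members. The charge items just before the ladder ask whether distributors would charge. The lead item then supposes that government pays them instead. In that sequence, free to the client is a natural reading, and on it the ladder works. This stands as far as it goes: the bids are ambiguous, not uninformative.

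A reader might therefore infer too much, namely that all seven items fail and that the minimum cannot be recovered from the questionnaire at all. The documents do not support that. One reasonable reading of the bids brackets the minimum, and three charge items, not one, supply an amount per kit.

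A reader might also infer that the protocol names the minimum acceptable payment as a target. It does not. The target follows from the term willingness to accept, which appears in section 2.1 and Appendix 5 but not in objectives 6 to 8 of section 2.2, the costing recruitment in section 5.3 or the cost analysis in section 7.4.

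One defence does not help. The note that response options may change when programmed introduces the cohort questionnaires in Appendix 3. It does not extend to Appendix 5, and it does not cover the wording of questions.

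**Conclusion.** The point holds in a limited form. The closing item asks for the wrong end of the scale. Answered as worded, it gives a value at or above the threshold, so any bias is upward and has no upper limit; this applies to that one item, not to every possible estimate. The five bids are interpretable only if every respondent takes free to mean free to the client, which the items do not say. The lead item's codes and the block's heading are plain drafting errors. As printed, the only unambiguous amounts per kit come from the three charge items, which are imperfect asking-price proxies.

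The conclusion rests on the ordinary meaning of willingness to accept as a minimum. The effect is confined to a secondary economic measure. The cohort primary outcome and sample size are not touched.

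**What to change.** Before fielding, change the payment block of Appendix 5 as follows:

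- **Closing item:** *What is the minimum amount per kit you would need to be paid to distribute kits free of charge to community members?*
- **Each of the five bids, x = 1 to 5:** *If the government paid you ZMW x per kit, would you agree to distribute kits free of charge to clients? Yes / No / Don't know.* The condition that kits stay free to clients must remain in the wording. Without it, a distributor could accept ZMW1 and still charge the client.
- **Lead item:** replace the codes with Yes / No / Don't know, and say to whom free applies.
- **Heading:** retitle the block as willingness to accept for payment.

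Randomising the order of the bids is a matter of preference and is not needed to cure the fault. The cost is the rewording of seven items (one lead, five bids, one closing) and one heading, with no extra interviews. Once answers have been collected under the printed wording, the two readings cannot be told apart.
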